6.1.1.1.2. Sensitivity/Supplementary Analyses

The main analysis will also be performed on the mITT population.

6.1.1.2. hSBA Titer for Each of the MenACWY Test Strains for ACWY-Experienced Participants

6.1.1.2.1. Main Analysis

- Estimand strategy: Hypothetical.
- Analysis set: ACWY-experienced participants: Post-Vaccination 1 evaluable population for Group 4 and post-Vaccination 2 evaluable population for Group 3.

- Analysis methodology: 95% CI for the difference in the percentage of seroresponders, calculated by the Miettinen and Nurminen procedure.
- Intercurrent events and missing data: Missing serology results will not be imputed. Participants will be summarized according to the vaccine group to which they were randomized.
- The 95% CIs for the difference in the percentage of seroresponders, defined as participants achieving a 4-fold rise from baseline for each MenACWY test strain, 1 month after Vaccination 2 in Group 3 compared to 1 month after Vaccination 1 in Group 4 will be calculated using the Miettinen and Nurminen method. The lower limit of the CI will be used in the hypothesis test for noninferiority as detailed in [Section 5.1](#). Exact 2-sided 95% CIs for the percentages of seroresponders will be provided using the Clopper-Pearson method.

6.1.1.2.2. Sensitivity/Supplementary Analyses

The main analysis will also be performed on the mITT population.

6.1.1.3. Primary MenB Test Strain Evaluation (A22, A56, B24, and B44)

6.1.1.3.1. Main Analysis

- Estimand strategy: Hypothetical.
- Analysis set: Post–Vaccination 2 evaluable population.
- Analysis methodology: 95% CI for the difference in the percentage of the 4-fold rises and composite responses, calculated by the Miettinen and Nurminen procedure.
- Intercurrent events and missing data: Missing serology results will not be imputed. Participants will be summarized according to the vaccine group to which they were randomized.
- The 95% CIs for the difference in the percentage of participants achieving an hSBA titer \geq LLOQ (1:16 for strain A22 and 1:8 for strains A56, B24, and B44) for all 4 primary MenB test strains combined (composite response), in Groups 1 and 3 combined compared to Groups 2 and 4 combined, at 1 month after Vaccination 2 will be calculated using the Miettinen and Nurminen method. The lower limit of the CI will be used in the hypothesis test for noninferiority as detailed in [Section 5.1](#).
- The 95% CIs for the difference in the percentage of participants achieving at least a 4-fold rise in hSBA titer from baseline for each of the 4 primary MenB test strains, in Groups 1 and 3 combined compared to Groups 2 and 4 combined, at 1 month after Vaccination 2 will be calculated using the Miettinen and Nurminen method. The lower limit of the CI will be used in the hypothesis test for noninferiority as detailed in [Section 5.1](#).

Exact 2-sided 95% CIs for the percentages of participants achieving 4-fold rises, and composite responses, will be provided using the Clopper-Pearson method.

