4. STUDY DESIGN

4.1. Overall Design

This is a Phase 3, randomized, active-controlled, observer-blinded multicenter trial in which approximately 2413 participants ≥ 10 to <26 years of age will be randomly assigned to receive either MenABCWY and saline, or Trumenba and MenACWY-CRM, as shown in [Table 1](#). The study will include evaluation of both ACWY-naïve and ACWY-experienced individuals. All participants will be naïve to any meningococcal group B vaccine prior to enrollment.

Participants in Groups 1 through 4 will be considered an immunogenicity subset, and will contribute to both the safety and immunogenicity analyses; these participants will have blood drawn prior to Vaccination 1 and 1 month after Vaccinations 1 and 2. Participants in Groups 5 through 8 will be considered a safety subset and will contribute to the safety analysis only, and will not have blood drawn for immunogenicity evaluations.

Randomization will be stratified by prior vaccination history. Overall, approximately 1225 ACWY-naïve and 1188 ACWY-experienced participants (having received 1 dose of Menactra or Menveo ≥ 4 years prior to the date of randomization) will be enrolled. Of these total participants, up to 675 ACWY-naïve and 1013 ACWY-experienced participants will contribute to the immunogenicity subset.

Participants enrolled in the immunogenicity subset will contribute to both immunogenicity and safety evaluations. Additionally, participants will be enrolled in a safety subset that will contribute exclusively to the safety evaluation. Numbers enrolled in the safety subset will therefore be based on numbers needed to achieve an overall number of enrolled participants, all of whom will contribute to the safety evaluation. Numbers stated in the protocol to be enrolled by group across immunogenicity and safety subsets ([Section 1.2](#) and [Table 1](#)) are estimates only.

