The second primary objective will be evaluated at 1 month following Vaccination 2 and the post-Vaccination 2 evaluable population will be used. The null hypothesis (H_0) for noninferiority for each primary MenB test strain is as follows:

$$H_0: \pi_{G1+G3} - \pi_{G2+G4} \leq -10\%$$

where π_{G1+G3} and π_{G2+G4} are the percentages of 4-fold rises and composite responses for Groups 1 and 3 combined and for Groups 2 and 4 combined, respectively, at 1 month after the second vaccination.

If the lower limit of the 2-sided 95% CI for the differences in 4-fold rises and composite responses (Group 1+3 – Group 2+4) is $> -10\%$ for all of the primary MenB test strains at 1 month after the second vaccination, the noninferiority of the MenABCWY regimen to the Trumenba regimen is declared.

If noninferiority for both the primary objectives is demonstrated, then an additional noninferiority evaluation of the ACWY response will be performed. This evaluation will be a secondary objective and will be conducted as for the primary ACWY noninferiority assessment; however, the secondary objective will be an evaluation of noninferiority of seroresponders who achieve a 4-fold rise at 1 month following Vaccination 1 for both groups evaluated (Group 1 versus Group 2 for ACWY-naïve and Group 3 versus Group 4 for ACWY-experienced).

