9.4.1. Immunogenicity Analyses

Primary	
For each of the 4 ACWY test strains, the difference in the percentages of seroresponders, defined as participants achieving a 4-fold rise from baseline, in Group 1 at 1 month after Vaccination 2 compared to Group 2 at 1 month after Vaccination 1, and also the difference in seroresponders in Group 3 at 1 month after Vaccination 2 compared to Group 4 at 1 month after Vaccination 1, will be calculated.
 
For each of the 4 primary MenB test strains, the differences of the 4-fold rises and composite responses of Groups 1 and 3 combined compared to Groups 2 and 4 combined at 1 month after Vaccination 2 will be calculated.
 
The Miettinen and Nurminen method will be used to derive the CI for the difference in percentages between vaccine groups. The lower limit of the CI will be used in the hypothesis test for noninferiority as detailed in Section 9.1.
 
The analysis for the ACWY test strains is based on the post-Vaccination 1 evaluable population for Groups 2 and 4 and on the post-Vaccination 2 evaluable population for Groups 1 and 3 and the analysis for the primary MenB strains is based on the post-Vaccination 2 evaluable population in order to provide a comparison that has the greatest chance of identifying a difference between the groups with respect to immunogenicity, if a meaningful difference in vaccine effect actually exists.
 
Exact 2-sided 95% CIs for the percentages (seroresponders, 4-fold-rises and composite responses) will be provided using the Clopper-Pearson method.
 
A supportive analysis will be performed based on the modified intent-to-treat (mITT) population. Participants will be summarized according to the vaccine group to which they were randomized. Missing serology data will not be imputed.

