4.1. Vaccine/Stratum Misallocation

- Randomized into the wrong MenACWY stratum: These participants will be included in the safety population for the safety analysis and will be reported under the MenACWY stratum according to true MenACWY history. These participants will also be included in the mITT population for immunogenicity analyses if data are available, and will be reported under the MenACWY stratum according to their true MenACWY history (MenACWY experience recorded on the CRF for prior MenACWY history). However, these participants will be excluded from the analyses using evaluable immunogenicity population(s) for the MenACWY endpoints, but included in the analyses using evaluable immunogenicity population(s) for the MenB endpoints. A participant's true MenACWY history (naïve/experienced) will be ascertained programmatically from the prior meningococcal vaccine data set in the clinical database before the planned unblinding. Serogroups contained within the prior meningococcal vaccine received will be determined by the sponsor's global medical monitor.
- Participants randomized to the safety subset but for whom immunogenicity data are collected according to the CRF: These participants will be reported according to their true immunogenicity subset per the CRF. A participant's true immunogenicity/safety assignment will be ascertained programmatically in the clinical database before the planned unblinding. These participants will be included in the safety population and the mITT population. For the evaluable populations, they will be excluded.

- Vaccinated but not randomized: These participants will be included in the safety population for safety analysis and will be reported under the vaccine group based on the vaccine received, but will be excluded from immunogenicity analyses.
- Randomized but not vaccinated: These participants will be included in the ITT population and excluded from any safety analyses. They may be included in the mITT population if any assay results are available and will be reported under their randomized group for immunogenicity analyses.
- Randomized but received incorrect vaccine: These participants will be included in the mITT population for immunogenicity analyses if data are available and will be reported under the vaccine group based on the randomized vaccine. These participants will also be included in the safety population for safety analysis and will be reported under the vaccine group based on the vaccine received.

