5.3.2. Immunogenicity Data

As assay data are expected to be missing completely at random, the primary analysis for the primary objectives will be based upon the observed, determinate observations. No imputation will be performed. The proportion of participants with missing immunogenicity data may be summarized at each blood sampling visit for each MenB and MenACWY strain. The denominator will be the as-randomized population. The category of missing reasons (QNS, indeterminate, not done, dropout) may also be summarized.

If 10% or more of the participants in any group have missing hSBA data for the MenB or MenACWY strains for non-withdrawal-related reasons, a sensitivity analysis using an MMRM in the immunogenicity subset may be applied for each strain (GMT). For the MenACWY strains, the ACWY-naïve and ACWY-experienced participants will be analyzed separately. For the primary MenB strains, Groups 1 and 3 combined will be described against Groups 2 and 4 combined.

The MMRM uses maximum likelihood estimation and it is under the assumption that the missingness is at random (MAR). To account for the intraparticipant correlation among the repeated measures, an unstructured covariance matrix will be used. In case the model does not converge, further covariance structures will be explored (ie, first-order autoregressive, compound symmetry). Independent variables (race, sex, etc) may be dropped from the model because of nonconvergence.

$\text{Log (hSBA)} = \text{randomized group(s)} + \text{race} + \text{sex} + \text{geographic location (US; ex-US)} + \text{age at randomization} + \text{visit}$. The intercept will be set as random effect.

In addition to type III analysis output, least-squares GMTs at each visit will be summarized for each strain.

These analyses will use the mITT population, using $\frac{1}{2}$ LLOQ to set the hSBA values below LLOQ.

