6.1.1.3.2. Sensitivity/Supplementary Analysis

The main analysis will also be performed on the mITT population if there is a difference of more than 10% between the evaluable immunogenicity and mITT populations.

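### The five primary MenB noninferiority CIs pool ACWY-naïve and ACWY-experienced participants; stratifying them by the ACWY history used in randomization would gain a little precision at no cost in participants

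*SAP*

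**What the plan says.** Protocol 4.1 states: "Randomization will be stratified by prior vaccination history". SAP 2.2 repeats this, and both documents add geographic region as a second factor.

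The MenB hypotheses do not use the history factor. In protocol 9.1.2 the two quantities compared "are the percentages of 4-fold rises and composite responses for Groups 1 and 3 combined and for Groups 2 and 4 combined", and SAP 5.1 agrees. For the method, protocol 9.4.1 says: "The Miettinen and Nurminen method will be used to derive the CI for the difference in percentages between vaccine groups". SAP 6.1.1.3.1 has the same: "Analysis methodology: 95% CI for the difference in the percentage of the 4-fold rises and composite responses, calculated by the Miettinen and Nurminen procedure". Neither document names strata or weights, and protocol Table 9 powers each endpoint as one comparison of 900 with 450 participants. That the CI is unstratified is inferred from this; the word itself is not used.

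No other MenB analysis brings history in:

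- The optional missing-data models in SAP 5.3.2 list no history term and keep the arms merged: "For the primary MenB strains, Groups 1 and 3 combined will be described against Groups 2 and 4 combined".
- The subgroups listed in SAP 6.4 are age, sex, race and ethnicity.

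SAP 4.1 bears on any stratified version. Participants randomized into the wrong ACWY stratum are "included in the analyses using evaluable immunogenicity population(s) for the MenB endpoints". In the mITT population they "will be reported under the MenACWY stratum according to their true MenACWY history". SAP 6.1.1.3.2 adds a conditional repeat: "The main analysis will also be performed on the mITT population if there is a difference of more than 10" percent between the evaluable and mITT populations.

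**The concern.** When a trial randomizes within strata, an analysis that ignores them treats between-stratum variation in response as noise. If MenB response differs by ACWY history, the pooled CI is wider than it needs to be.

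The pooled estimate also depends on the two arms having the same naïve share. That share is equal by design at enrollment, but the analysis set is what remains after an assumed 20% loss, so chance can move the pooled difference in either direction. The mITT repeat has a further route to imbalance. SAP 4.1 admits participants randomized to the safety subset for whom immunogenicity data exist, and that subset is planned at 500:50 in naïve and 125:50 in experienced participants, not 2:1. How many there would be is unknown.

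The second primary objective is where precision counts most. All five MenB endpoints must pass, and its stated power (above 91.6%) is the lowest of the three primary comparisons. B24 (95.64%) and the composite (97.80%) are its weakest endpoints.

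**Working it through.** **Inputs** (protocol 9.2.1 and Table 9)

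- Evaluable numbers: 360, 180, 540 and 270 in Groups 1 to 4. Enrolled: 450, 225, 675 and 338, with 20% nonevaluable.
- Margin −10 points, two-sided 95% CI, assumed true difference 0.
- Control rates: A22 73.8%, A56 95%, B24 64.5%, B44 86.4%, composite 72.9%.
- Assumed, because the documents give no MenB rate by history: an experienced-minus-naïve gap of 0, 10, 20 or 30 points around the same overall rate, the same in both arms. Thirty is an extreme.

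**The plan's own figure.** The product of the Table 9 powers is 0.9803 × 0.9999 × 0.9564 × 0.9994 × 0.9780 = 0.9163, as stated. Simulating the unstratified Miettinen-Nurminen test at 900 vs 450 gives A22 98.1%, A56 about 100%, B24 95.7%, B44 99.96% and composite 97.9%, with product 91.9%. Table 9 therefore reproduces as an unstratified analysis.

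**Planned bias.** The naïve share is 360/900 = 0.40 and 180/450 = 0.40. The shares are equal, so there is no planned bias.

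**Weights.** The Mantel-Haenszel weight is n₁n₂/(n₁+n₂):

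- naïve: 360 × 180/540 = 120
- experienced: 540 × 270/810 = 180

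As shares these are 0.40 and 0.60, which equal the pooled mix. At the planned numbers the weighted difference is the pooled difference.

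**Precision, approximately.** The variance ratio of stratified to pooled is 1 − 0.4 × 0.6 × gap²/[p(1−p)]. For B24, p(1−p) = 0.645 × 0.355 = 0.2290. The pooled half-width is 1.96 × √[0.2290 × (1/900 + 1/450)] = 5.41 points.

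| Gap (points) | Variance ratio | Stratified half-width (points) |
|---|---|---|
| 10 | 0.9895 | 5.39 |
| 20 | 0.9581 | 5.30 |
| 30 | 0.9057 | 5.15 |

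**Simulation.** This used the score statistic with restricted maximum likelihood and the N/(N−1) factor at −10 points, 1,000,000 trials per setting. At the planned evaluable numbers, B24 power over the four gaps is 95.7, 95.8, 96.0 and 96.4% pooled against 95.7, 95.9, 96.4 and 97.1% stratified. The gains, from unrounded values, are 0, 0.1, 0.3 and 0.7 points.

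With evaluability drawn as binomial 80% of the enrolled numbers, B24 gives:

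| Gap (points) | Power pooled | Power stratified | Gain (points) | One-sided type I error pooled | Stratified |
|---|---|---|---|---|---|
| 0 | 0.9570 | 0.9569 | 0 | 0.0256 | 0.0256 |
| 10 | 0.9574 | 0.9587 | 0.1 | 0.0248 | 0.0254 |
| 20 | 0.9592 | 0.9636 | 0.4 | 0.0232 | 0.0253 |
| 30 | 0.9626 | 0.9717 | 0.9 | 0.0209 | 0.0252 |

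The composite and A22 gain at most 0.5 points. Product power over the five endpoints is 91.8, 91.9, 92.4 and 93.1% pooled against 91.8, 92.2, 93.3 and 94.9% stratified. The product assumes independence, applies the gap to A22, B24 and the composite, and keeps A56 and B44 at their Table 9 values.

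**Chance imbalance.** With a common difference d and naïve shares s₁ and s₂, the pooled difference is d − (s₁ − s₂) × gap. Under random loss the SD of s₁ − s₂ is about √[0.24 × 0.20 × (1/900 + 1/450)] = 0.0126; simulation gives 1.27 points. The pooled difference then moves with an SD of 0.13, 0.25 and 0.38 points at gaps of 10, 20 and 30. The stratified estimate does not move for this reason.

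**Two checks on the stratified CI (B24)**

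- True differences unequal across strata but averaging −10 (naïve −16 to −4, experienced −6 to −14, gaps 0 to 20): one-sided type I error 0.0247 to 0.0260.
- An assumed 5% of participants in the wrong stratum, analysed as randomized: gains of 0.1, 0.4 and 0.8 points at gaps of 10, 20 and 30, with type I error 0.025.

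**The case against.** The strongest objection is that nothing is broken. Hypothesis, CI and power agree across both documents, the pooled CI is valid, and where response differs by history it is the more conservative of the two. The gain depends on a gap that the documents do not support. All participants are MenB-vaccine-naïve, and the only immunogenicity difference by history that the protocol draws attention to is in ACWY titers. At a 10-point gap the B24 half-width falls only from 5.41 to 5.39. The product power overstates precision, because the composite is built from the same strain titers as the other endpoints. Region is also a randomization factor and is left out. The change also touches a primary hypothesis and brings in a stratum rule that pooling does not need. A stratified CI offered only as supportive would be lighter.

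Most of this stands as a limit on size. The gain is small, it is zero if there is no gap, and the product figures are only indicative. It does not make the change unsound: stratifying loses nothing at gap 0 and holds type I error near 0.025. Region is a fair point. The documents give group sizes by history but only an approximate 80/20 split by region, so the weights and target under a region-by-history scheme cannot be checked in the same way, and no gain from region was computed. The lighter option would show dependence on history but would leave the primary CI without the gain.

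**Conclusion.** The point holds as an improvement, not as an error. The five primary MenB CIs ignore ACWY history although randomization uses it, and no other planned MenB analysis takes it up. Using it costs no participants and no power. For B24 under random 20% loss it adds 0.1 points of power at a 10-point gap, 0.4 at 20 and 0.9 at 30, and nothing at 0. It also removes sensitivity to chance imbalance in the naïve share.

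These sizes rest on assumed gaps that are equal in both arms, a true difference of 0 for power, and loss unrelated to arm or history. No bias or type I error inflation is claimed against the current plan. The change is worth making, but the trial does not depend on it.

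**What to change.** - **Method.** In SAP 6.1.1.3.1 and protocol 9.4.1, make the CIs for the four 4-fold rises and the composite Miettinen-Nurminen intervals stratified by ACWY history with Mantel-Haenszel weights. Keep the pooled CI as supportive.
- **Hypothesis.** In protocol 9.1.2 and SAP 5.1, state the MenB null on the weighted difference. At the planned numbers it equals the pooled difference, so the −10% margin keeps its meaning.
- **Stratum rule.** Use the stratum as randomized for everyone in this analysis. That includes wrong-stratum participants kept under SAP 4.1 and any mITT repeat under SAP 6.1.1.3.2. Add to SAP 4.1 that this differs from the true-history reporting used elsewhere in the mITT population.
- **Unchanged.** Leave the ACWY CIs, margin, alpha and sample size as they are, and do not add region.

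The cost is wording in SAP 4.1, 5.1, 6.1.1.3.1 and 6.1.1.3.2 and in protocol 9.1.2 and 9.4.1, plus programming the stratified form of the method already chosen. Protocol section 9 requires an amendment for major changes to a primary analysis, so one may be needed. No new data are required. All of it should be settled before unblinding.

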6.1.1.3.2. Sensitivity/Supplementary Analysis

The main analysis will also be performed on the mITT population if there is a difference of more than 10% between the evaluable immunogenicity and mITT populations.

6.1.2. Primary Safety Endpoints

Safety endpoints will be summarized by MenABCWY groups (Groups 1, 3, 5, and 7 combined) and Trumenba groups (Groups 2, 4, 6, and 8 combined). The reactogenicity data may also be summarized by true MenACWY history (naïve/experienced).

6.1.2.1. Local Reactions Within 7 Days After Vaccination

- Analysis set: Safety. Refer to [Section 4](#) for visit-specific populations.
- Analysis methodology: Descriptive summary statistics and Clopper-Pearson CIs.
- Intercurrent events and missing data: Participants will be analyzed according to the vaccine they actually received. Missing e-diary data will not be imputed.
- For each group, n, %, and 95% CI will be presented by vaccine group for the following variables:
 - Presence or absence of each local reaction on any day (Days 1-7) after vaccination.
 - Presence or absence of any local reaction on any day (Days 1-7) after vaccination.
 - Maximum severity of each local reaction on any day (Days 1-7) after vaccination.

6.1.2.2. Systemic Events Within 7 Days After Vaccination

- Analysis set: Safety. Refer to [Section 4](#) for visit-specific populations.
- Analysis methodology: Descriptive summary statistics and Clopper-Pearson CIs.
- Intercurrent events and missing data: Participants will be analyzed according to the vaccine they actually received. Missing e-diary data will not be imputed.
- For each group, n, %, and 95% CI will be presented by vaccine group for the following variables:
 - Presence or absence of each systemic event on any day (Days 1-7) after vaccination.
 - Presence or absence of any systemic event on any day (Days 1-7) after vaccination.
 - Maximum severity of each systemic event on any day (Days 1-7) after vaccination.

